7.2 Rationale

In January 2016, the PRAC reviewed the effectiveness of the PPP for oral isotretinoin. This review noted post-marketing data and published studies raising concerns about how well the requirements of the PPP are followed in clinical practice. These data suggested that there were a number of areas that may impact the effectiveness of the PPP including inconsistencies in information provided with regard to contraceptive measures and a lack of up-to-date information about the most effective contraceptive methods; inadequate documentation of the required patient monitoring, and potential differences in the PPPs implemented across the generics. Consequently, the PRAC identified a need for a detailed assessment of compliance with the requirements of the PPP and initiated the Art 31 referral for all retinoids (Procedure number: EMEA/H/A-31/1446).

As outcome of the Art. 31 referral on retinoids, the PRAC (endorsed by CHMP and European Commission [EC]) has requested a DUS (category 1 study) and a complementary survey (category 3 study) to assess the effectiveness of the updated RMMs. The study design should aim to evaluate and quantify the effectiveness of the updated RMM, which should include a pre- and post-implementation analysis and assessment. This protocol describes the DUS. The survey is described in a separate protocol.

8. RESEARCH QUESTION AND OBJECTIVES

The aim of the DUS is to address the following research question: Is there a difference in physicians' prescribing and monitoring practice in the periods before and after the update of the pregnancy prevention programme (PPP) for the oral retinoids acitretin, alitretinoin, and isotretinoin when treating women of childbearing potential?

The objectives of the DUS are:

Primary objective:

To evaluate the changes in the prescribing and monitoring practices following the update of the PPP in females of childbearing potential receiving prescriptions of the oral retinoids acitretin, alitretinoin, or isotretinoin by comparing the following key elements of the PPP between the pre- and the post-implementation period:

- Contraceptives* before, during, and after treatment with oral retinoids
- Time interval between prescription dates for oral retinoids during treatment episode
- Laboratory pregnancy tests – where available - before, during, and after treatment with oral retinoids

* contraceptive methods that require prescription and which are, therefore, captured in the administrative databases

Secondary objectives:

- To describe the patient profile during the pre-and the post-implementation period, with respect to:
 - Patient age
 - Indication for oral retinoids
- To describe the prescriber specialty during the pre-and the post-implementation period
- To describe the exposure characteristics during the pre-and the post-implementation period, with respect to:
 - Active substance
 - Dose
 - Treatment duration
- To describe the incidence of pregnancies exposed to oral retinoids during the pre-and the post-implementation period
- To stratify the key elements of the PPP described in the primary objective by oral retinoid substance
- To describe trends in the physician's prescribing and monitoring practice of oral retinoids with respect to measures of the PPP (contraceptive use and performance of pregnancy tests) over the entire duration the study

9. RESEARCH METHODS

9.1 Study Design

This is a multicounty, multisource, observational cohort study in females of childbearing potential receiving oral retinoids (i.e., acitretin, alitretinoin and isotretinoin) using established data sources in different European countries (i.e., France, Germany, Spain, and Sweden)

The study will employ a pre-post design to evaluate the effectiveness of the implementation of the updated RMMs with respect to the PPP according to the following schedule:

- Pre-implementation period: period prior to the date of the implementation of the updated RMMs
- Post-implementation period: period after the implementation of the updated RMMs

Periods will be defined as (also see Figure 1):

Pre-implementation period: The period before the implementation of the updated RMMs. The RMM tools will be distributed in the fourth quarter 2018 (the exact date may vary depending on the country). The pre-implementation period captures two periods:

- Pre-referral: the 2-year period before referral start in July 2016. This period will be used for the before and after comparison with the post-implementation period.
- Post-referral: the 2.5-year period between the referral start date in July 2016 and the distribution of the RMM tools in the target countries (assumed until December 2018). The duration of this period may vary depending on the duration of the approval and the distribution of the RMM tools in each country.

Post-implementation period: This period captures the time starting after the distribution of EM until December 2020. The start date of the period in each country will depend on the date on which the EM is approved by the respective national competent authorities.

The final dates of the study periods depend on the final schedule of the implementation of the updated RMMs in each country.

Figure 1: Overview of study periods

A single database for all target countries is not available. Therefore, a study approach was chosen which includes multiple data sources to gather drug utilisation data for oral retinoids (acitretin, alitretinoin and isotretinoin) in the European countries of interest.

Databases with longitudinal secondary patient data collected continuously over time will be used preferably to provide the most comprehensive data for the outcomes of interest.

To gather drug utilisation data for oral retinoids (acitretin, alitretinoin and isotretinoin) before and after an update of measures for pregnancy prevention, the following types of patient-level longitudinal databases, which are commonly used for post-authorisation safety studies (PASS) with respect to drug utilisation, are considered:

- Claims data
- National registries
- Primary care databases

9.2 Setting

Oral retinoids acitretin, alitretinoin, and isotretinoin are marketed in a broad range of countries in the Europe. Countries for the DUS were selected based on the following criteria:

- Countries in which the number of exposed patients is high based on market share
- Coverage of different regions in Europe
- Availability and accessibility of patient-level databases
- Availability of the information required to meet the study objectives

Based on these criteria and also taking the sales data (see Table 2) into account, the following countries will be included in the DUS: France, Germany, Spain, and Sweden, the latter representing an EU country from the Northern part of Europe and a data source of national coverage which is well-established in pharmacovigilance research.

Table 2: Top countries based on volume sales (retail and hospital) for the oral retinoids acitretin, alitretinoin and isotretinoin, by country (01/2017 to 12/2017): Source: IQVIA MIDAS June 2018

Country	ACITRETIN	ALITRETINOIN	ISOTRETINOIN	Grand Total
FRANCE	2.97%	0.22%	11.97%	15.15%
UK	3.86%	0.20%	9.57%	13.63%
SPAIN	1.62%	0.02%	8.54%	10.19%
POLAND	0.81%	0.00%	9.00%	9.82%
GERMANY	0.94%	0.50%	8.11%	9.54%
NETHERLANDS	1.01%	0.37%	6.19%	7.56%
ITALY	1.65%	0.01%	3.64%	5.30%
GREECE	0.27%	0.00%	3.88%	4.15%
BELGIUM	0.47%	0.00%	3.23%	3.70%
PORTUGAL	0.41%	0.00%	2.37%	2.78%
AUSTRIA	0.17%	0.07%	2.12%	2.36%
SWEDEN	0.20%	0.00%	2.10%	2.30%
NORWAY	0.17%	0.08%	1.88%	2.13%
FINLAND	0.22%	0.01%	1.70%	1.93%
DENMARK	0.15%	0.02%	1.72%	1.89%

9.2.1 Inclusion Criteria

The following criteria must be met to be included in the study:

- Female gender
- Childbearing potential (13-49 years of age, inclusive)
- Received or was prescribed at least one prescription of the oral retinoids acitretin, alitretinoin, or isotretinoin in either the pre-implementation or post-implementation period

9.2.2 Exclusion Criteria

All females in the age group 13 to 49 years with available information that they are not of childbearing potential before initiation of oral retinoids (such as records of hysterectomy or sterilisation) will be excluded.

Data for the oral retinoids acitretin, alitretinoin, and isotretinoin will only be extracted from databases in target countries where the respective active substance has been granted market authorisation.

No further exclusion criteria will be applied.

9.3 Variables

To meet the objectives of the DUS, the selection of variables was done with respect to the key elements requested by the PRAC as far as they are captured in established data sources.

9.3.1 Exposure Definition and Measures

Exposure will be defined as one or more prescriptions of oral retinoids (issued or dispensed) during one of the pre-defined study periods. These prescriptions will be identified using the Anatomical Therapeutic Chemical Classification System (ATC) for the target substances or the International non-proprietary name system (INN).

The exposure start date for each patient will be defined as the first prescription/dispensing record of an oral retinoids treatment episode during the pre-defined time periods. Because this study aims to assess the prescribing behaviour of HCPs, should both the prescription and the dispensing date be recorded, the prescription date would be used preferentially.

Exposure will be described by prescription length, duration of treatment and (average) daily dose and will be provided by active substance.

It will be assumed that all prescriptions and their associated dates recorded in the databases reflect actual prescription fills and subjects will start treatment at the exposure start date.

The following variables will be extracted from the data sources:

- Active substance
- Date of prescription (or dispensing)
- Pack size or days' supply
- Dosage strength
- Recommended daily dose (if available)

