All medicines are prescribed electronically in Sweden. The National Prescription Register tracks the full details of all dispensed medications at individual patient-level in Sweden since July 1, 2005. Patients are followed longitudinally through their personal identification number, regardless of which pharmacy they visit. The National Drug Register is updated monthly and covers all sales from Swedish pharmacies.

The available data in the National Drug Register include:

- Patient demographics (age, gender, and residency)
- Prescription information (date of prescription, prescriber's specialty, WHO ATC code, and brand name)
- Dispatch information (dispatch date, product number, total dose dispatched, number of packages dispatched, and drug cost)
- Product information (Package size, formulation, etc.)

Information on prescribed dose is only documented in free text format where available, and days' supply is not recorded.

In Sweden, the online database on prescription held by the National Board of Health and Welfare provides the following information on the annual prevalence of Swedish women aged 15-49 years who filled at least one prescription for hormonal contraceptives in 2012-2017: ATC G02B contraceptives for topical use: 4.3-5.4%; ATC G03A hormonal contraceptives for systemic use: 22.4-26.1% (reference: prescription registry).

Of note, to gain access to the linked register an approval from the local ethical review board is necessary, whereby the research project and ethical aspects should be explained in a formal application. The ethics approval is dependent on the data being made publicly available in some form. Please see below for more detailed information on the information contained in each register.

The Medical Birth Register contains information on 97% to 99.4% of all pregnancies resulting in delivery in Sweden and is frequently used for quality work and for research (National Board of Health and Welfare, Sweden 2012; Olausson PO, 2002). The register contains detailed information about mothers and new-borns. However, pregnancies are only captured after 22 weeks. The identification and timing of pregnancies will be done according to published methodology (Stephansson et al. 2018).

Records on pregnancies are also documented in the National Patient Register regardless of the duration of pregnancy, but missing information regarding early termination needs to be taken into account.

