9.7.3.2 Exposure

The following variables of exposure will be analysed:

Prescription length

The length of prescription will be determined by the date of prescription (or prescription fill/dispensing) plus the expected number of days of supply based on the days' supply reported with this prescription or, when not available, pack size and the recommended daily dose by the physician (if available) or, by default, according to the information of strength connected with the prescription and SmPC. The length will be provided in days.

The following analyses will be performed:

- Average length of prescriptions per treatment episode
- Overall number of prescriptions per patient

Duration of treatment

The duration of treatment will be analysed through the recorded prescriptions in the databases. The date of the first prescription issued (or filled) will be considered as treatment start date. End of treatment duration will be defined by the date of the last prescription plus the number of days' supply of this last prescription. Consecutive prescriptions of oral retinoids will be considered as one treatment episode (allowed gaps between prescriptions will be provided in the statistical analysis plan). The duration of treatment episodes will be provided in days.

The following analyses will be performed:

- Duration of treatment episodes
- Number of prescriptions per treatment episode
- Number of treatment episodes per patient

Average daily dose

The average daily dose will be analysed over a treatment episode based on dosage strength, pack size or day supply and number of prescriptions per episode.

9.7.3.3 *Pregnancy and pregnancy outcomes*

The following analyses will be performed for the pre-implementation and the post-implementation periods:

- Number of pregnancies exposed to oral retinoids
- Incidence rate of pregnancies exposed to oral retinoids
- Information on pregnancy outcome (i.e., live births, termination, stillbirth, miscarriage, or recorded birth defect) will be provided when available in the databases

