If the information on trimester, start date of pregnancy, or delivery/end of pregnancy date is available, the pregnancy will be considered exposed if at least one oral retinoid prescription was recorded in the period between the assumed dates of pregnancy start and delivery/end of pregnancy. In case information on pregnancy trimester or start date or delivery/end of pregnancy date is not available in the data source, a pregnancy will be considered as exposed to oral retinoids if at least one oral retinoid prescription was issued within 90 days before or within 180 days after the first record of a given pregnancy.

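### Dating exposure by prescription rather than dispensing can leave a Swedish retinoid dispatch made during pregnancy counted as unexposed

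*Protocol*

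**What the plan says.** Protocol 9.3.1 defines exposure through prescriptions issued or dispensed and then ranks the two dates: "should both the prescription and the dispensing date be recorded, the prescription date would be used preferentially". The reason given is "Because this study aims to assess the prescribing behaviour of HCPs". The section goes on to assume that recorded dates "reflect actual prescription fills and subjects will start treatment at the exposure start date". Its list of variables to extract has one date item, the prescription date, with dispensing in brackets.

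For Sweden, 9.4.3.1 lists two groups of fields: "Prescription information (date of prescription, prescriber's specialty, WHO ATC code, and brand name") and, separately, "Dispatch information (dispatch date, product number, total dose dispatched, number of packages dispatched, and drug cost"). Days' supply is not recorded there.

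Two later rules depend on the date chosen:
- **Treatment stop (9.7.3.2):** "End of treatment duration will be defined by the date of the last prescription plus the number of" days that this last prescription supplies.
- **Exposed pregnancy, timing known (9.7.3.3):** a pregnancy is exposed "if at least one oral retinoid prescription was recorded in the period between the assumed dates of pregnancy start" and its end.

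If timing is unknown, 9.7.3.3 looks for a prescription issued from 90 days before to 180 days after the first pregnancy record. Neither sensitivity analysis in 9.7.4 uses dispensing dates.

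**The concern.** One date serves two purposes. When a physician prescribed is the right clock for the interval between prescriptions and for checks made before prescribing. Whether a pregnancy was exposed, and when treatment ended, depends on when the woman had the drug. In Sweden the register dates that event, but the preference in 9.3.1 sets the date aside.

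The incidence of exposed pregnancies is a stated secondary objective, and Sweden has the largest patient count in Table 5 (20,580, footnoted as non-unique patients). The during-treatment and after-treatment contraception and test measures in 9.7.2 also hang on the stop date.

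**Working it through.** The protocol states no figure on this point, so there is nothing to reproduce. The check follows the rules through one case and then shows how the result moves under stated assumptions.

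**Does the rule apply in Sweden?** Yes. 9.4.3.1 lists both dates, so the preference for the prescription date takes effect.

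**Which pregnancy rule applies?** 9.4.3.1 commits Sweden to a published method for timing pregnancies. The timing-known rule therefore normally governs, and the 90-day look-back does not.

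**The case.** A prescription is dated before conception and the drug is dispatched after it. The prescription date lies outside the pregnancy and the dispatch date inside. 9.7.3.3 does not carry supply forward, so the pregnancy is unexposed by prescription date and exposed by dispatch date. One delayed collection is enough. The mirror case (prescribed in pregnancy, collected after its end) is also possible, which is a further reason to report both versions.

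**Illustration with a single collection.** Assumptions, none from the documents: prescription on day 0, dispatch on day d, 30 days' supply, and pregnancy equally likely to start on any day from prescription to end of supply.
- Stop by prescription date = 0 + 30 = day 30. Stop by dispatch date = day d + 30. The stop is early by d days.
- Pregnancies with a dispatch inside but the prescription outside are those starting on days 1 to d, so the share is d / (d + 30).

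| Assumed lag d | Stop early by | Share scored unexposed despite a dispatch in pregnancy |
|---|---|---|
| 0 days | 0 days | 0/30 = 0% |
| 14 days | 14 days | 14/44 = 32% |
| 30 days | 30 days | 30/60 = 50% |

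The remaining pregnancies in each row start after dispatch. Neither date falls inside them, so the choice of date does not alter their classification.

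**Illustration with repeat collections.** Assume k collections of 30 days on one prescription. The stop by dispatch date is d + 30k.
- If only the last dispatch's supply is added to the prescription date, the stop is day 30, early by d + 30(k − 1).
- If all collected supply is added, the stop is day 30k, early by d only.

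For k = 3 and d = 14 the dispatch-based stop is day 104. The error is 104 − 30 = 74 days under the first method and 104 − 90 = 14 days under the second. The pregnancy misclassification does not depend on which method is used.

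These figures show direction and sensitivity. They are not estimates for Sweden.

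**The case against.** **Scope.** The preference sentence stands in the paragraph on exposure start. 9.3.1 speaks of prescriptions issued or dispensed, 9.7.3.2 allows issued or filled, and a recorded prescription in 9.7.3.3 could be read to include a dispatch. This stands in part, since the text can be read that way. But the preference is worded generally, the timing-unknown rule refers to issue, and nothing in 9.7.3.3 says that a dispatch date counts.

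**Deliberate choice.** The research question concerns physicians' practice, and the fill assumption is disclosed. Germany records a date of prescription and SIDIAP holds prescribed medication, so the prescription date aligns Sweden with both. This stands for the prescriber outcomes and the main cross-country analysis.

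**Before-after comparison.** The same rule applies in both periods. If the undercounted proportion is equal in each, the ratio of incidences is unaffected. The absolute incidence, which the protocol sets out to describe, is still too low.

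A reader might also infer more than the documents support:
- **A stop date that is early by a month or more, so that the two-month after-treatment window lies largely or wholly on treatment.** With supply counted per dispatch, this needs repeat collection, which is not documented. 9.7.3.2 adds the supply of the last prescription, not of the last dispatch, and Table 1 lists prescription length as limited, or ideally limited, to 30 days.
- **Different clocks in the pooled estimate because French claims record dispensing.** Table 3 lists the date of prescription as available for France.
- **Many Swedish tests moved from before to during treatment.** 9.9.2 says Swedish tests appear only when ICD-10 coded, and 9.4.3.1 says primary care is absent. This gives no reason to redefine the 7-day pre-treatment window.

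**Conclusion.** The point holds in a limited form. The prescription-date preference is sound for prescription intervals and pre-treatment checks. Applied to 9.7.3.3 in Sweden, it can classify a pregnancy as unexposed although the register dates a dispatch inside it, so exposed pregnancies can be undercounted. Treatment stop falls early by at least the lag from prescription to dispatch, taking treatment to begin at dispatch. It falls earlier than that only with repeat collection and per-dispatch supply.

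The size is unknown because the documents give neither the lag nor the frequency of repeat collection. With immediate single collection the error is nil, and it grows with the lag. The conclusion rests on reading the 9.3.1 preference as governing 9.7.3.2 and 9.7.3.3. If that is not intended, the protocol should say so.

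**What to change.** - **9.3.1:** extract both the prescription and the dispensing date wherever held. Keep the prescription date for prescription intervals, for anchoring the pre-treatment test and contraception checks, and for the main cross-country analysis.
- **9.7.3.3:** count a pregnancy as exposed if either a prescription date or a dispensing date falls in the pregnancy window. Report the prescription-date version beside it.
- **9.7.4:** add a Swedish sensitivity analysis that dates supply, treatment stop and the during- and after-treatment windows by dispensing.

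The cost is a few sentences and a little extra analysis, since both fields are already in the Swedish register. The drawback is that Swedish pregnancy exposure would be ascertained slightly differently from sources with only a prescription date, which is why both versions should be shown. The change should precede the Swedish data request: under 9.6 the data come through a study-specific application form, and a request for one date only would leave the dispatch date out of the study data set.

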9.3.2 Patient age and prescribing and monitoring practices

To describe the prescribing and monitoring practices of oral retinoids before and after the dissemination of risk minimisation measures, the following variables will be considered:

- Patient age
- Specialty of prescriber (not for France)
- Records of sterilisation in the medical history
- Indication for oral retinoid prescription (only available for in-hospital prescriptions in France)
 - Diagnoses coded by International Classification of Diseases (ICD)-10 (i.e., acne, severe hand eczema, psoriasis, or other dermatological conditions oral retinoids are indicated, for code list please refer to Appendix 3)
- Contraceptives before, during and after oral retinoid treatment
 - Prescription of hormonal contraceptives (date of prescription/dispensing, type, pack size or days' supply)
 - Prescription of intrauterine devices (IUD) (date of prescription/dispensing or procedure)
- Laboratory pregnancy tests – based on availability - before, during and after oral retinoid treatment
 - Laboratory pregnancy tests (blood or urine) recorded in the databases (type, if available, and date of test)
 - Records (ICD-10 codes related to an exam) which document the performance of a laboratory pregnancy test (date of record)

